	0DQ67ZZ	Repair Stomach, Via Natural or Artificial Opening
	0DQ68ZZ	Repair Stomach, Via Natural or Artificial Opening Endoscopic
	0DV64CZ	Restriction of Stomach with Extraluminal Device, Percutaneous Endoscopic Approach
	0DW643Z	Revision of Infusion Device in Stomach, Percutaneous Endoscopic Approach
	0DW64CZ	Revision of Extraluminal Device in Stomach, Percutaneous Endoscopic Approach
	0D190Z9	Bypass Duodenum to Duodenum, Open Approach
	0D190ZA	Bypass Duodenum to Jejunum, Open Approach
	0D190ZB	Bypass Duodenum to Ileum, Open Approach
	0D190ZL	Bypass Duodenum to Transverse Colon, Open Approach
	0D194Z9	Bypass Duodenum to Duodenum, Percutaneous Endoscopic Approach
	0D194ZA	Bypass Duodenum to Jejunum, Percutaneous Endoscopic Approach
	0D194ZB	Bypass Duodenum to Ileum, Percutaneous Endoscopic Approach
	0D194ZL	Bypass Duodenum to Transverse Colon, Percutaneous Endoscopic Approach
	0D198Z9	Bypass Duodenum to Duodenum, Via Natural or Artificial Opening Endoscopic
	0D198ZA	Bypass Duodenum to Jejunum, Via Natural or Artificial Opening Endoscopic
	0D198ZB	Bypass Duodenum to Ileum, Via Natural or Artificial Opening Endoscopic
	0D198ZL	Bypass Duodenum to Transverse Colon, Via Natural or Artificial Opening Endoscopic
	0D1A0ZA	Bypass Jejunum to Jejunum, Open Approach
	0D1A0ZB	Bypass Jejunum to Ileum, Open Approach
	0D1A0ZH	Bypass Jejunum to Cecum, Open Approach
	0D1A0ZK	Bypass Jejunum to Ascending Colon, Open Approach
	0D1A0ZL	Bypass Jejunum to Transverse Colon, Open Approach
	0D1A0ZM	Bypass Jejunum to Descending Colon, Open Approach
	0D1A0ZN	Bypass Jejunum to Sigmoid Colon, Open Approach
	0D1A0ZP	Bypass Jejunum to Rectum, Open Approach
	0D1A4ZA	Bypass Jejunum to Jejunum, Percutaneous Endoscopic Approach

PFIZER CONFIDENTIAL

Type	Codes	Description
	0D1A4ZB	Bypass Jejunum to Ileum, Per cutaneous Endoscopic Approach
	0D1A4ZH	Bypass Jejunum to Cecum, Per cutaneous Endoscopic Approach
	0D1A4ZK	Bypass Jejunum to Ascending Colon, Percutaneous Endoscopic Approach
	0D1A4ZL	Bypass Jejunum to Transverse Colon, Percutaneous Endoscopic Approach
	0D1A4ZM	Bypass Jejunum to Descending Colon, Percutaneous Endoscopic Approach
	0D1A4ZN	Bypass Jejunum to Sigmoid Colon, Percutaneous Endoscopic Approach
	0D1A4ZP	Bypass Jejunum to Rectum, Percutaneous Endoscopic Approach
	0D1A8ZA	Bypass Jejunum to Jejunum, Via Natural or Artificial Opening Endoscopic
	0D1A8ZB	Bypass Jejunum to Ileum, Via Natural or Artificial Opening Endoscopic
	0D1A8ZH	Bypass Jejunum to Cecum, Via Natural or Artificial Opening Endoscopic
	0D1A8ZK	Bypass Jejunum to Ascending Colon, Via Natural or Artificial Opening Endoscopic
	0D1A8ZL	Bypass Jejunum to Transverse Colon, Via Natural or Artificial Opening Endoscopic
	0D1A8ZM	Bypass Jejunum to Descending Colon, Via Natural or Artificial Opening Endoscopic
	0D1A8ZN	Bypass Jejunum to Sigmoid Colon, Via Natural or Artificial Opening Endoscopic
	0D1A8ZP	Bypass Jejunum to Rectum, Via Natural or Artificial Opening Endoscopic
	0D1B0ZB	Bypass Ileum to Ileum, Open Approach
	0D1B0ZH	Bypass Ileum to Cecum, Open Approach
	0D1B0ZK	Bypass Ileum to Ascending Colon, Open Approach
	0D1B0ZL	Bypass Ileum to Transvers e Colon, Open Approach
	0D1B0ZM	Bypass Ileum to Descending Colon, Open Approach
	0D1B4ZN	Bypass Ileum to Sigmoid Colon, Percutaneous Endoscopic Approach
	0D1B4ZP	Bypass Ileum to Rectum, Percutaneous Endoscopic Approach
	0D1B4ZQ	Bypass Ileum to Anus, Percutaneous Endoscopic Approach
	0D1B8ZB	Bypass Ileum to Ileum, Via Natural or Artificial Opening Endoscopic
	0D1B8ZH	Bypass Ileum to Cecum, Vi a Natural or Artificial Opening Endoscopic

Type	Codes	Description
	0D1B8ZK	Bypass Ileum to Ascending Colon, Via Natural or Artificial Opening Endoscopic
	0D1B8ZL	Bypass Ileum to Transverse Colon, Via Natural or Artificial Opening Endoscopic
	0D1B8ZM	Bypass Ileum to Descending Colon, Via Natural or Artificial Opening Endoscopic
	0D1B8ZN	Bypass Ileum to Sigmoid Colon, Via Natural or Artificial Opening Endoscopic
	0D1B8ZP	Bypass Ileum to Rectum, Via Natural or Artificial Opening Endoscopic
	0D1B8ZQ	Bypass Ileum to Anus, Via Natural or Artificial Opening Endoscopic

Table 10. Charlson Comorbidity Index Score Calculation

Condition	ICD-9 Code(s)	ICD-10 Code(s)	Point
Myocardial Infarction	410.xx; 412.xx	I21, I22, I252	1
Congestive Heart Failure	428.xx	I43, I50, I099, I110, I130, I132, I255, I420, I425, I426, I427, I428, I429, P290	1
Peripheral vascular disease	441.xx; 443.9x; 785.4x; v43.4x, procedure : 38.48	I70, I71, I731, I738, I739, I771, I790, I792, K551, K558, K559, Z958, Z959	1
Cerebrovascular disease	430.xx-438.99 Modified to remove 430.xx-432.xx	G45, G46, I60, I61, I62, I63, I64, I65, I66, I67, I68, I69, H340	1
Dementia	290.xx	F00, F01, F02, F03, G30, F051, G311	1
Chronic obstructive pulmonary disease	490.xx-496.99; 500.xx-505.99; 506.4x	J40, J41, J42, J43, J44, J45, J46, J47, J60, J61, J62, J63, J64, J65, J66, J67, I278, I279, J684, J701, J703	1
Rheumatologic disease	710.0x-710.19; 710.4x-; 714.0x-714.29; 714.81; 725.xx	M05, M32, M33, M34, M06, M315, M351, M353, M360	1
Peptic ulcer disease	531.0x-531.79; 532.4x-532.79; 533.4x-533.79; 534.0x-534.79; 531.9x; 532.9x; 533.9x; 534.9x Modified to remove: 531.00, 531.01, 531.20, 531.21, 531.40, 531.41, 531.60, 531.61 532.40, 532.41, 532.60, 532.61 533.40, 533.41, 533.60, 533.61, 534.00, 534.01, 534.20, 534.21, 534.40, 534.41, 534.60, 534.61	K25, K26, K27, K28	1

Condition	ICD-9 Code(s)	ICD-10 Code(s)	Point
Mild liver disease	571.2x; 571.4x-571.69	B18, K73, K74, K700, K701, K702, K703, K709, K717, K713, K714, K715, K760, K762, K763, K764, K768, K769, Z944	1
Diabetes (mild to moderate)	250.0x-250.39, 250.7x	E100, E101, E106, E108, E109, E110, E111, E116, E118, E119, E120, E121, E126, E128, E129, E130, E131, E136, E138, E139, E140, E141, E146, E148, E149	1
Diabetes + complications	250.4x-250.69	E102, E103, E104, E105, E107, E112, E113, E114, E115, E117, E122, E123, E124, E125, E127, E132, E133, E134, E135, E137, E142, E143, E144, E145, E147	2
Hemiplegia or paraplegia	342.xx; 344.1x	G81, G82, G041, G114, G801, G802, G830, G831, G832, G833, G834, G839	2
Renal disease	582.xx; 583.0x-583.79; 585.xx-586.99; 588.xx	N18, N19, N052, N053, N054, N055, N056, N057, N250, I120, I131, N032, N033, N034, N035, N036, N037, Z490, Z491, Z492, Z940, Z992	2
Any malignancy, including lymphoma and leukemia	140.xx-172.99; 174.xx-195.99; 200.xx-208.99	C00, C01, C02, C03, C04, C05, C06, C07, C08, C09, C10, C11, C12, C13, C14, C15, C16, C17, C18, C19, C20, C21, C22, C23, C24, C25, C26, C30, C31, C32, C33, C34, C37, C38, C39, C40, C41, C43, C45, C46, C47, C48, C49, C50, C51, C52, C53, C54, C55, C56, C57, C58, C60, C61, C62, C63, C64, C65, C66, C67, C68, C69, C70, C71, C72, C73, C74, C75, C76, C81, C82, C83, C84, C85, C88, C90, C91, C92, C93, C94, C95, C96, C97	2
Moderate/severe liver disease	456.0x-456.29; 572.2x-572.89 Modified to remove: 456.0x, 456.20	K704, K711, K721, K729, K765, K766, K767, I850, I859, I864, I982	3
Metastatic solid tumor	196.xx-199.99	C77, C78, C79, C80	6
AIDS	042.xx-044.99	B20, B21, B22, B24	6

Table 11. Baseline Comorbidities

Covariates	ICD-9-CM/CPT/HCPCS Codes	ICD-10-CM Codes
History Stroke/SE	Same as the outcome stroke/SE (Table 12)	Same as the outcome stroke/SE (Table 12)
History of Bleeding	Same as the outcome major bleeding (Table 12)	Same as the outcome major bleeding (Table 12)
Congestive Heart Failure (CHF)	398.91, 402.x1, 404.x3, 428.xx	I0981, I110, I132, I501, I5020, I5021, I5022, I5023, I5030, I5031, I5032, I5033, I5040, I5041, I5042, I5043, I509
Diabetes	250.xx, 357.2, 362.0, 366.41	E08311, E08319, E083211, E083212, E083213, E083219, E083291, E083292, E083293, E083299, E083311, E083312, E083313, E083319, E083391, E083392, E083393, E083399, E083411, E083412, E083413, E083419, E083491, E083492, E083493, E083499, E083511, E083512, E083513, E083519, E083521, E083522, E083523, E083529, E083531, E083532, E083533, E083539, E083541, E083542, E083543, E083549, E083551, E083552, E083553, E083559, E083591, E083592, E083593, E083599, E0836, E0840, E0842, E09311, E09319, E093211, E093212, E093213, E093219, E093291, E093292, E093293, E093299, E093311, E093312, E093313, E093319, E093391, E093392, E093393, E093399, E093411, E093412, E093413, E093419, E093491, E093492, E093493, E093499, E093511, E093512, E093513, E093519, E093521, E093522, E093523, E093529, E093531, E093532, E093533, E093539, E093541, E093542, E093543, E093549, E093551, E093552, E093553, E093559, E093591, E093592, E093593, E093599, E0936, E0940, E0942, E1010, E1011, E1021, E1022, E1029, E10311, E10319, E103211, E103212, E103213, E103219, E103291, E103292, E103293, E103299, E103311, E103312, E103313, E103319, E103391, E103392, E103393, E103399, E103411, E103412, E103413, E103419, E103491, E103492, E103493, E103499, E103511, E103512, E103513, E103519, E103521, E103522, E103523, E103529, E103531, E103532, E103533, E103539, E103541, E103542, E103543, E103549, E103551, E103552, E103553, E103559, E103591, E103592, E103593, E103599, E1036, E1037X1, E1037X2, E1037X3, E1037X9, E1039, E1040, E1041, E1042, E1043, E1044, E1049, E1051, E1052, E1059, E10610, E10618, E10620, E10621, E10622, E10628, E10630, E10638, E10641, E10649, E1065, E1069, E108, E109, E1100, E1101, E1121, E1122, E1129, E11311, E11319, E113211, E113212, E113213, E113219, E113291, E113292, E113293, E113299, E113311, E113312,

Covariates	ICD-9-CM/CPT/HCPCS Codes	ICD-10-CM Codes
		E113313, E113319, E113391, E113392, E113393, E113399, E113411, E113412, E113413, E113419, E113491, E113492, E113493, E113499, E113511, E113512, E113513, E113519, E113521, E113522, E113523, E113529, E113531, E113532, E113533, E113539, E113541, E113542, E113543, E113549, E113551, E113552, E113553, E113559, E113591, E113592, E113593, E113599, E1136, E1137X1, E1137X2, E1137X3, E1137X9, E1139, E1140, E1141, E1142, E1143, E1144, E1149, E1151, E1152, E1159, E11610, E11618, E11620, E11621, E11622, E11628, E11630, E11638, E11641, E11649, E1165, E1169, E118, E119, E1300, E1301, E1310, E1311, E1321, E1322, E1329, E13311, E13319, E133211, E133212, E133213, E133219, E133291, E133292, E133293, E133299, E133311, E133312, E133313, E133319, E133391, E133392, E133393, E133399, E133411, E133412, E133413, E133419, E133491, E133492, E133493, E133499, E133511, E133512, E133513, E133519, E133521, E133522, E133523, E133529, E133531, E133532, E133533, E133539, E133541, E133542, E133543, E133549, E133551, E133552, E133553, E133559, E133591, E133592, E133593, E133599, E1336, E1337X1, E1337X2, E1337X3, E1337X9, E1339, E1340, E1341, E1342, E1343, E1344, E1349, E1351, E1352, E1359, E13610, E13618, E13620, E13621, E13622, E13628, E13630, E13638, E13641, E13649, E1365, E1369, E138, E139, E0851, E0852, E0951, E0952, E1051, E1052, E1151, E1152, E1351, E1352, E1359, E13610, E13618, E13620, E13621, E13622, E13628, E13630, E13638, E13641, E13649, E1365, E1369, E138, E139
Hypertension	401.xx -405.xx	I10, I110, I119, I120, I129, I130, I1310, I1311, I132, I150, I151, I152, I158, I159, I160, I161, I169, N262
Renal Disease	582.xx; 583.0x-583.79; 585.xx-586.99; 588.xx	B520, E0821, E0822, E0829, E0921, E0922, E0929, I120, I129, I130, I1310, I1311, I132, M3214, M3215, M3504, N000, N001, N002, N003, N004, N005, N006, N007, N008, N009, N010, N011, N012, N013, N014, N015, N016, N017, N018, N019, N020, N021, N022, N023, N024, N025, N026, N027, N028, N029, N030, N031, N032, N033, N034, N035, N036, N037, N038, N039, N040, N041, N042, N043, N044, N045, N046, N047, N048, N049, N050, N051, N052, N053, N054, N055, N056, N057, N058, N059, N060, N061, N062, N063, N064, N065, N066

Covariates	ICD-9-CM/CPT/HCPCS Codes	ICD-10-CM Codes
		N067, N068, N069, N070, N071, N072, N073, N074, N075, N076, N077, N078, N079, N08, N140, N141, N142, N143, N144, N150, N158, N159, N16, N170, N171, N172, N178, N179, N181, N182, N183, N184, N185, N186, N189, N19, Z992, Z9115, Z4931, Z4901, Z4902, Z4931, Z4932, Z4932 Procedure codes: 5A1D00Z, 5A1D60Z, 05HY33Z, 06HY33Z, 03130ZD, 03140ZD, 03150ZD, 03160ZD, 03170ZD, 03180ZD, 03190ZF, 031A0ZF, 031B0ZF, 031C0ZF, 031209D, 031209F, 03120AD, 03120AF, 03120JD, 03120JF, 03120KD, 03120KF, 03120ZD, 03120ZF, 031309D, 031309F, 03130AD, 03130AF, 03130JD, 03130JF, 03130KD, 03130KF, 03130ZD, 03130ZF, 031409D, 031409F, 03140AD, 03140AF, 03140JD, 03140JF, 03140KD, 03140KF, 03140ZD, 03140ZF, 031509D, 031509F, 03150AD, 03150AF, 03150JD, 03150JF, 03150KD, 03150KF, 03150ZD, 03150ZF, 031609D, 031609F, 03160AD, 03160AF, 03160JD, 03160JF, 03160KD, 03160KF, 03160ZD, 03160ZF, 031709D, 031709F, 03170AD, 03170AF, 03170JD, 03170JF, 03170KD, 03170KF, 03170ZD, 03170ZF, 031809D, 031809F, 03180AD, 03180AF, 03180JD, 03180JF, 03180KD, 03180KF, 03180ZD, 03180ZF, 031909F, 03190AF, 03190JF, 03190KF, 03190ZF, 031A09F, 031A0AF, 031A0JF, 031A0KF, 031A0ZF, 031B09F, 031B0AF, 031B0JF, 031B0KF, 031B0ZF, 031C09F, 031C0AF, 031C0JF, 031C0KF, 031C0ZF, 03PY07Z, 03PY0JZ, 03PY0KZ, 03PY37Z, 03PY3JZ, 03PY3KZ, 03PY47Z, 03PY4JZ, 03PY4KZ, 03130JD, 03140JD, 03150JD, 03160JD, 03170JD, 03180JD, 03190JF, 031A0JF, 031B0JF, 031C0JF, 3E1M39Z
Liver Disease	570-573	K70-K77
Myocardial Infarction	410.xx, 412.xx	I2101, I2102, I2109, I2111, I2119, I2121, I2129, I213, I214, I220, I221, I222, I228, I229, I252
Dyspepsia or Stomach Discomfort	787.1: Heartburn	
	789.0: Abdominal Pain	R100, R1010-R1012
	789.4: Abdominal Rigidity	
	789.6: Abdominal Tenderness	
	536.8: Dyspepsia	K30, R1013, R102, R10811, R10812, R10813, R10814, R10816, R10817, R10819, R10821, R10822, R10826, R10827, R10829, R1084, R109, R12, R1930, R1931, R1932, R1936, R1937

Covariates	ICD-9-CM/CPT/HCPCS Codes	ICD-10-CM Codes
Peripheral artery disease	440.xx-445.xx	I700, I701, I70201, I70202, I70203, I70208, I70209, I70211, I70212, I70213, I70218, I70219, I70221, I70222, I70223, I70228, I70229, I70231, I70232, I70233, I70234, I70235, I70238, I70239, I70241, I70242, I70243, I70244, I70245, I70248, I70249, I7025, I70261, I70262, I70263, I70268, I70269, I70291, I70292, I70293, I70298, I70299, I70301, I70302, I70303, I70308, I70309, I70311, I70312, I70313, I70318, I70319, I70321, I70322, I70323, I70328, I70329, I70331, I70332, I70333, I70334, I70335, I70338, I70339, I70341, I70342, I70343, I70344, I70345, I70348, I70349, I7035, I70361, I70362, I70363, I70368, I70369, I70391, I70392, I70393, I70398, I70399, I70401, I70402, I70403, I70408, I70409, I70411, I70412, I70413, I70418, I70419, I70421, I70422, I70423, I70428, I70429, I70431, I70432, I70433, I70434, I70435, I70438, I70439, I70441, I70442, I70443, I70444, I70445, I70448, I70449, I7045, I70461, I70462, I70463, I70468, I70469, I70491, I70492, I70493, I70498, I70499, I70501, I70502, I70503, I70508, I70509, I70511, I70512, I70513, I70518, I70519, I70521, I70522, I70523, I70528, I70529, I70531, I70532, I70533, I70534, I70535, I70538, I70539, I70541, I70542, I70543, I70544, I70545, I70548, I70549, I7055, I70561, I70562, I70563, I70568, I70569, I70591, I70592, I70593, I70598, I70599, I70601, I70602, I70603, I70608, I70609, I70611, I70612, I70613, I70618, I70619, I70621, I70622, I70623, I70628, I70629, I70631, I70632, I70633, I70634, I70635, I70638, I70639, I70641, I70642, I70643, I70644, I70645, I70648, I70649, I7065, I70661, I70662, I70663, I70668, I70669, I70691, I70692, I70693, I70698, I70699, I70701, I70702, I70703, I70708, I70709, I70711, I70712, I70713, I70718, I70719, I70721, I70722, I70723, I70728, I70729, I70731, I70732, I70733, I70734, I70735, I70738, I70739, I70741, I70742, I70743, I70744, I70745, I70748, I70749, I7075, I70761, I70762, I70763, I70768, I70769, I70791, I70792, I70793, I70798, I70799, I708, I7090, I7091, I7092, I7100, I7101, I7102, I7103, I711, I712, I713, I714, I715, I716, I718, I719, I720, I721, I722, I723, I724, I725, I726, I728, I729, I7300, I7301, I731, I7381, I7389, I739, I742, I743, I744, I75011, I75012, I75013, I75019, I75021, I75022, I75023, I75029, I7770, I7771, I7772, I7773, I7774, I7775, I7776, I7777, I7779, I790, I791, I798

Covariates	ICD-9-CM/CPT/HCPCS Codes	ICD-10-CM Codes
Non-stroke/SE peripheral vascular disease	440, 441, 442, 443	I70-I73, I77-I79
Transient ischemic attack (TIA)	435.x	G458, G459, Z8673
Coronary artery disease	410.xx-414.xx	I200, I201, I208, I209, I2101, I2102, I2109, I2111, I2119, I2121, I2129, I213, I214, I220, I221, I222, I228, I229, I240, I241, I248, I249, I2510, I25110, I25111, I25118, I25119, I252, I253, I2541, I2542, I255, I256, I25700, I25701, I25708, I25709, I25710, I25711, I25718, I25719, I25720, I25721, I25728, I25729, I25730, I25731, I25738, I25739, I25750, I25751, I25758, I25759, I25760, I25761, I25768, I25769, I25790, I25791, I25798, I25799, I25810, I25811, I25812, I2582, I2583, I2584, I2589, I259
Anemia and coagulation defects	280.xx-286.xx	D50-D53, D55-D59, D60-D69,

Table 12. Clinical Outcomes

Outcome Variables		ICD-9-CM/Procedure Codes	ICD-10-CM Codes/Procedure Codes
Stoke/ SE	Hemorrhagic Stroke	430.xx-432.xx Cases will be excluded if traumatic brain injury (ICD-9: 800-804, 850-854) was present during hospitalization.	I6000, I6001, I6002, I6010, I6011, I6012, I602, I6030, I6031, I6032, I604, I6050, I6051, I6052, I606, I607, I608, I609, I610, I611, I612, I613, I614, I615, I616, I618, I619; Cases will be excluded according to Table 12.
	Ischemic Stroke	433.x1, 434.x1, 436	I6300, I63011, I63012, I63013, I63019, I6302, I63031, I63032, I63033, I63039, I6309, I6310, I63111, I63112, I63113, I63119, I6312, I63131, I63132, I63133, I63139, I6319, I6320, I63211, I63212, I63213, I63219, I6322, I63231, I63232, I63233, I63239, I6329, I6330, I63311, I63312, I63313, I63319, I63321, I63322, I63323, I63329, I63331, I63332, I63333, I63339, I63341, I63342, I63343, I63349, I6339, I6340, I63411, I63412, I63413, I63419, I63421, I63422, I63423, I63429, I63431, I63432, I63433, I63439, I63441, I63442, I63443, I63449, I6349, I6350, I63511, I63512, I63513, I63519, I63521, I63522, I63523, I63529, I63531, I63532, I63533, I63539, I63541, I63542, I63543, I63549, I6359, I636, I638, I639, I6789
	Systemic	444.x, 445.x	I7401, I7409, I7410, I7411, I7419, I742, I743,

Outcome Variables		ICD-9-CM/Procedure Codes	ICD-10-CM Codes/Procedure Codes
	Embolism		I744, I745, I748, I749, I75011, I75012, I75013, I75019, I75021, I75022, I75023, I75029, I7581, I7589
Major Bleeding	Major Gastrointestinal bleeding event	456.0, 456.20, 530.82, 531.0x, 531.2x, 531.4x, 531.6x, 532.0x, 532.2x, 532.4x, 532.6x, 533.0x, 533.2x, 533.4x, 533.6x, 534.0x, 534.2x, 534.4x, 534.6x, 535.01, 535.11, 535.21, 535.31, 535.41, 535.51, 535.61, 537.83, 562.02, 562.03, 562.12, 562.13, 568.81, 569.3, 569.85, 578.x; Procedure Code: 44.43	I8501, I8511, K2211, K226, K250, K252, K254, K256, K260, K262, K264, K266, K270, K272, K274, K276, K280, K282, K284, K286, K2901, K2921, K2931, K2941, K2951, K2961, K2971, K2981, K2991, K31811, K3182, K5521, K5701, K5711, K5713, K5721, K5731, K5733, K5741, K5751, K5753, K5781, K5791, K5793, K625, K6381, K661, K920, K921, K922, K9161, K9162, K91840, K91841
	Major Intracranial Hemorrhage (ICH)	430, 431, 432.0, 432.1, 432.9, 852.0x, 852.2x, 852.4x, 853.0x	I6000, I6001, I6002, I6010, I6011, I6012, I602, I6030, I6031, I6032, I604, I6050, I6051, I6052, I606, I607, I608, I609, I610, I611, I612, I613, I614, I615, I616, I618, I619, I6200, I6201, I6202, I6203, I621, I629, S06340A, S06341A, S06342A, S06343A, S06344A, S06345A, S06346A, S06347A, S06348A, S06349A, S06350A, S06351A, S06352A, S06353A, S06354A, S06355A, S06356A, S06357A, S06358A, S06359A, S06360A, S06361A, S06362A, S06363A, S06364A, S06365A, S06366A, S06367A, S06368A, S06369A, S064X0A, S064X1A, S064X2A, S064X3A, S064X4A, S064X5A, S064X6A, S064X7A, S064X8A, S064X9A, S065X0A, S065X1A, S065X2A, S065X3A, S065X4A, S065X5A, S065X6A, S065X7A, S065X8A, S065X9A, S066X0A, S066X1A, S066X2A, S066X3A, S066X4A, S066X5A, S066X6A, S066X7A, S066X8A, S066X9A
	Major Other hemorrhage	285.1, 360.43, 362.43, 362.81, 363.61, 363.62, 363.72, 364.41, 372.72, 374.81, 376.32, 377.42, 379.23, 423.0x, 596.7x, 599.7x, 602.1x, 620.1, 621.4, 626.2, 626.5, 626.7, 626.8, 626.9, 719.1x, 782.7, 784.7, 784.8, 786.3x, 958.2, 997.02, 998.11; Procedure codes: 99.04	D62, D7801, D7802, D7821, D7822, E3601, E3602, E89810, E89811, G9731, G9732, G9751, G9752, H05231, H05232, H05233, H05239, H1130, H1131, H1132, H1133, H2100, H2101, H2102, H2103, H31301, H31302, H31303, H31309, H31311, H31312, H31313, H31319, H31411, H31412, H31413, H31419, H3560, H3561, H3562, H3563, H35731, H35732, H35733, H35739, H4310, H4311, H4312, H4313, H44811, H44812, H44813, H44819, H47021, H47022, H47023, H47029, H59111, H59112, H59113, H59119, H59121, H59122, H59123, H59129, H59311, H59312, H59313, H59319,

Outcome Variables	ICD-9-CM/Procedure Codes	ICD-10-CM Codes/Procedure Codes
		H59321, H59322, H59323, H59329, H9521, H9522, H9541, H9542, I312, I97410, I97411, I97418, I9742, I97610, I97611, I97618, I97620, J9561, J9562, J95830, J95831, L7601, L7602, L7621, L7622, M2500, M25011, M25012, M25019, M25021, M25022, M25029, M25031, M25032, M25039, M25041, M25042, M25049, M25051, M25052, M25059, M25061, M25062, M25069, M25071, M25072, M25073, M25074, M25075, M25076, M2508, M96810, M96811, M96830, M96831, N421, N857, N897, N920, N923, N930, N938, N939, N9961, N9962, N99820, N99821, R040, R041, R042, R0489, R049, R233, R310, R319, R58, T792XXA; Procedure codes: 30230N1, 30230P1, 30233N1, 30233P1, 30240N1, 30240P1, 30243N1, 30243P1, 30250N1, 30250P1, 30253N1, 30253P1, 30260N1, 30260P1, 30263N1, 30263P1

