9.2.2. Exclusion Criteria

Patients meeting any of the following criteria will not be included in the study:

- Had medical claims indicating a diagnosis or procedure of rheumatic mitral valvular heart disease, heart valve replacement/transplant, venous thromboembolism, or transient AF 6 months prior to or on the index date.
- Had hip/knee replacement surgery within 6 weeks prior to or on the index date.
- Were pregnant during the study period.
- Had an OAC prescription during the 6 months pre-index date.
- Had follow-up time equal to 0 days.
- Had more than one OAC on the index date.

Flag: A flag will be created to evaluate the mechanical heart valve/mitral stenosis during the 6 months prior to or on the index date using narrow definition.

All codes for the selection criteria are detailed in Appendix [Table 4](#).

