17. ANNEX 2. ADDITIONAL INFORMATION

17.1. Appendix

Table 4. Exclusion Criteria

Diagnosis	ICD-9 Code	ICD-10 Code
Valvular Heart Disease	394.0, 394.1, 394.2, 394.9, 396.0, 396.1, 396.8, 396.9, 424.0, 745.xx	I050, I051, I052, I058, I059, I080, I088, I089, I340, I341, I342, I348, I349, Q213, Z952, Z953, Z954
Mechanical Heart Valve/ Mitral Stenosis (narrow definition)	ICD-9-CM: 996.02, 996.71, 394.0, 394.2, 396.0, 396.1, 746.5 ICD-9 procedure: 35.20, 35.22, 35.24, 36.23, 35.97 CPT: 33405, 92987, 33427, 33426, 33425, 33422, 33420, 33430	ICD- 10 diagnosis codes: T82.01XA, T82.02XA, T82.03XA, T82.09XA, T82.817A- T82.897A, T82.9XXA, I05.0, I05.2, I08.0, Q23.2 ICD-10 Procedure Codes: 02RF07Z, 02RF08Z, 02RF0JZ, 02RF0KZ, 02RF37H, 02RF37Z, 02RF38H, 02RF38Z, 02RF3JH, 02RF3JZ, 02RF3KH, 02RF3KZ, 02RF47Z, 02RF48Z, 02RF4JZ, 02RF4KZ, 02RG07Z, 02RG08Z, 02RG0JZ, 02RG0KZ, 02RG37H, 02RG37Z, 02RG38H, 02RG38Z, 02RG3JH, 02RG3JZ, 02RG3KH, 02RG3KZ, 02RG47Z, 02RG48Z, 02RG4JZ, 02RG4KZ, 02RH07Z, 02RH08Z, 02RH0JZ, 02RH0KZ, 02RH37H, 02RH37Z, 02RH38H, 02RH38Z, 02RH3JH, 02RH3JZ, 02RH3KH, 02RH3KZ, 02RH47Z, 02RH48Z, 02RH4JZ, 02RH4KZ, 02RJ07Z, 02RJ08Z, 02RJ0JZ, 02RJ0KZ, 02RJ47Z, 02RJ48Z, 02RJ4JZ, 02RJ4KZ, 02UG3JZ, X2RF03Z, X2RF33Z, X2RF43Z

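### The Table 4 codes for the mitral valve exclusion omit 396.2, 396.3, I081 and I083, so patients whose only baseline mitral code is one of these stay in the cohort

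*Combined protocol and SAP*

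**What the plan says.** Section 9.2.2 sets the criterion: "Had medical claims indicating a diagnosis or procedure of rheumatic mitral valvular heart disease", in the six months up to and including the index date. It then states that "All codes for the selection criteria are detailed in Appendix" Table 4, so that table is the working definition.

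In Appendix 17.1, the Valvular Heart Disease row of Table 4 has two cells:

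- ICD-9: "394.0, 394.1, 394.2, 394.9, 396.0, 396.1, 396.8, 396.9, 424.0, 745.xx"
- ICD-10: "I050, I051, I052, I058, I059, I080, I088, I089, I340, I341, I342, I348, I349, Q213, Z952, Z953, Z954"

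A separate narrow-definition row covers mechanical valves and mitral stenosis. Its ICD-9 diagnosis codes are "996.02, 996.71, 394.0, 394.2, 396.0, 396.1, 746.5", and from the I08 family it has only I08.0. Section 9.2.2 gives this row a different role: "A flag will be created to evaluate the mechanical heart valve/mitral stenosis". It marks patients and does not remove them.

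The plan gives no reason for leaving any code out of the Valvular Heart Disease row.

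**The concern.** The exclusion is part of what makes the cohort non-valvular, as the study title promises. A code list that is narrower than the written criterion lets in patients whom the protocol declares ineligible, and they enter the apixaban versus warfarin comparison. A programmer who follows Table 4 exactly would produce this result without any error of their own.

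The identification period, July 2013 to December 2017, is served by both an ICD-9 and an ICD-10 list. If the lists have different holes, who is eligible depends partly on which coding system recorded the lesion. Little downstream is designed to pick this up. The comorbidity flags in Table 1 include no valve-disease variable, and the narrow flag lacks the same four codes.

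**Working it through.** There is no planned figure to reproduce. The check is whether each code of the two families appears in the rows of Table 4.

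| Code | Valvular Heart Disease row (exclusion) | Narrow row (flag only) | Transient AF row (exclusion) |
|---|---|---|---|
| 396.0 | yes | yes | no |
| 396.1 | yes | yes | no |
| 396.2 | **no** | no | no |
| 396.3 | **no** | no | no |
| 396.8 | yes | no | no |
| 396.9 | yes | no | no |
| I080 | yes | yes | no |
| I081 | **no** | no | no |
| I082 | no | no | no |
| I083 | **no** | no | no |
| I088 | yes | no | no |
| I089 | yes | no | no |

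The VTE, valve replacement, hip/knee and pregnancy rows contain no 396 or I08 code.

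**Could a wildcard cover them?** No. The ICD-9 cell uses a wildcard for 745 but lists the 396 codes one by one. The ICD-10 cell has neither a wildcard nor a range.

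**What do the codes mean?** Table 4 does not print titles, so this step uses the standard classification that the protocol adopts.

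- 396.2 is mitral insufficiency with aortic stenosis.
- 396.3 is mitral with aortic insufficiency.
- I08.1 is mitral plus tricuspid disease.
- I08.3 is mitral, aortic and tricuspid disease.
- I08.2 is aortic plus tricuspid. Its absence fits a mitral exclusion, and it is not part of this point.

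**Could the omission be deliberate, limiting the row to stenosis?** That does not fit. The row also lists 394.1, 424.0, I051 and I340, which are mitral insufficiency codes.

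**Who is kept?** Any one listed code in the window excludes the patient. Those wrongly kept are therefore patients whose only mitral code in the window is 396.2, 396.3, I081 or I083.

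**Do the two coding systems agree?** Not fully. Mitral plus aortic disease coded only as 396.2 or 396.3 is kept, but the same kind of disease coded I080 is excluded.

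**Scale.** The documents give no prevalence. As an assumption only, suppose 0.1% to 2% of the feasibility population in Section 9.5 carries an omitted code and no listed one:

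- About 56,000 patients in all: 0.001 × 56,000 = 56, and 0.02 × 56,000 = 1,120.
- About 20,000 apixaban patients: 0.001 × 20,000 = 20, and 0.02 × 20,000 = 400.

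The 56,000 is the whole feasibility population with a BMI or weight on record. It is not the obese apixaban and warfarin set used for Aim 3, so the counts there would be lower at the same prevalence.

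**The case against.** The strongest reply is that the gap is narrow. The row catches most combined mitral codes, as well as the listed single-valve mitral codes (394.x, 424.0, I05x, I34x). A patient with an omitted code who also has a listed one is still removed. This stands. A reader might infer from the gap that combined mitral disease in general remains in the cohort, but the list does not do that.

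Second, the contrast between coding systems relies on code titles and coding habits that the documents do not set out. Table 4 has no titles and no crosswalk. Mitral plus tricuspid disease shows the difficulty. One can argue that it is caught under ICD-9 through a separate mitral code and missed under ICD-10 as I081, but a separate I05x or I34x code could equally catch it under ICD-10. This stands too. The supportable statement is that eligibility can differ by coding system, not that it always does.

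Third, a reader might infer that the weighting cannot deal with the leak. The plan does not support that. Section 9.7.1 leaves the propensity covariates open, to be chosen on clinical rationale. Index year, heart failure, CHA2DS2-VASc and digoxin use are all Table 1 variables. They may adjust in part. They do not replace a valve-disease covariate, which Table 1 lacks.

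None of this explains why the four codes are missing.

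**Conclusion.** The point holds as a mismatch between the written criterion and its code list. The absence of the four codes can be verified in the text. That they name the mitral valve rests on the standard ICD titles.

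The consequence is limited to patients with no other listed code in the window. Their number is unknown, and the range of 56 to 1,120 is illustrative only. It is tempting to go further and say that the hazard ratio is biased in favour of apixaban. That would need the prevalence of these codes in each arm and the excess event risk they carry, and the documents give neither. Size and direction cannot be derived, and the effect may be small. The correction is worth making because it is cheap and brings the list into line with the protocol's own rule.

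**What to change.** In the Valvular Heart Disease row of Table 4, add 396.2 and 396.3 to the ICD-9 cell and I081 and I083 to the ICD-10 cell. Rerun the attrition step and report the number of patients removed by index year and by treatment, so that any imbalance can be seen rather than assumed.

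The cost is four codes and one rerun step. The sample loss should be small and falls only on patients whom Section 9.2.2 already makes ineligible. If the omission was intended, state the reason in Section 9.2.2 and report the same counts.
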